#### 3.1.1.2. Part A2 Dose Expansion

Part A2 monotherapy dose expansion phase will randomize HCC patients 1:1 to flat dose levels of either 30 mg (Arm 1) or 250 mg (Arm 2) of PF-04518600 given every 2 weeks up to 20 patients per arm. These are doses chosen based on the following preliminary data from Part A1.

- 1. Partial responses were observed in 1 melanoma and 1 HCC patient at 0.1 (n=10) and 0.3 mg/kg (n=11) dose levels. Full receptor occupancy in peripheral T cells was observed in both responders.
- 2. Full receptor occupancy was achieved for all patients at doses  $\geq 0.3$  mg/kg.

The flat dose that is equivalent to 0.3 mg/kg was determined to be 25 mg in terms of matching the center of the distributions based on the population PK/PD analysis using preliminary data from Part A1 of this study. However, 30 mg was chosen as the low dose (Arm 1) for Part A2 to ensure the 5th percentile of trough concentrations (Ctrough) to be at or above which the full receptor occupancy was observed.

Although no responses were observed in the 3 mg/kg cohort, increases in peripheral blood central memory CD4 T cell proliferation and activation similar to the increases found at the 0.1 mg/kg were observed at 3 mg/kg. Therefore, Arm 2 will evaluate a 3 mg/kg flat dose equivalent of 250 mg.

An additional flat dose level of 800 mg, approximately equivalent to 10 mg/kg, may be added after initiation of enrollment into Arms 1 and 2 if this is supported by emerging data from the 10 mg/kg cohort of Part A1.

All patients in A2 will undergo mandatory pre- and on-treatment biopsies (See Schedule of Activities for specifics).

If preliminary sign of efficacy from Part A1, or emerging data from other OX40 agonist programs indicate a rationale for exploration of a different tumor type, these may be added or substituted for HCC patients.

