# 9.3.1. Part A Monotherapy

The number of patients to be enrolled in the study will depend upon the observed safety profile, which will determine the number of patients at each dose level and the number of dose levels explored.

At least 9 patients will be treated at the dose declared as the MTD. If MTD was not reached by definition of safety criteria, this statement will apply for highest tested dose level.

The sample size using the mTPI approach cannot be determined in advance. It is estimated the number of DLT evaluable patients to be enrolled in the dose escalation stage will allow a reliable and accurate estimate of the MTD.

The exact sample size of the mTPI design in Part A1 cannot be pre specified in advance because it is a dynamic feature of the design. The maximum sample size after which the Part A1 will be stopped and MTD declared is 58 patients. Also, a minimum of 9 patients is required to establish the MTD. The actual sample size of Part A1 will depend on the underlying dose toxicity profile and variability in actual data realization.

As for the number of patients treated at each dose, it is expected that the typical number will be 2 to 4 patients for the doses actually studied. For the dose declared as MTD at the end of Part A1, this number will be at least 9 patients.

The planned sample size for Part A2 expansion cohort is up to 40 evaluable patients. An evaluable patient will have both a baseline and on-treatment tumor biopsy. Aggregate toxicity will be monitored for patients in Part A2. DLT will continue to be assessed in Part A2, and data acquired in Part A1 dose-escalation phase and Part A2 dose expansion phase will be combined to assess the toxicity (as suggested by Lasonos and O'Quigley, 2014). In the event the observed toxicity exceeds 30%, a revised MTD may be recommended.

Although the A2 sample size is not based on any statistical considerations, the study would have 69% power to assess an overall response rate of 10% with 20 patients assuming the overall response rate of current therapy is 2%,  $^{96}$  using a one-sample test under a two-sided  $\alpha$  level of 0.1. The study would have about 93% power if the true response rate is 20%. A table of 90% confidence intervals based on observed number of responders is provided below for reference:

Table 7. 90% Confidence Intervals of Overall Response I	Rate
---	------

	N=20	90% Confidence Interval		
Observed Responders	ORR	Lower Limit	Upper Limit	
0*	0	0	5.6%	
1	5%	0	15.5%	

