2	10%	0	23.5%	
4	20%	2.8%	37.2%	
6	30%	10.6%	49.4%	
8	40%	19.5%	60.5%	

\*: with 0.005 continuity correction for confidence interval calculation

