# 9.4. Efficacy Analysis

In this FIP study, anti-tumor clinical activity is a secondary objective.

Tumor response in terms of time to progression, tumor progression, duration of response, and best objective response by RECIST and irRECIST will be summarized. Summary tables of response rates, median time to progression and corresponding confidence intervals will be provided Summary tables and figures will be generated by dose levels and/or tumor types. Data will be presented in the form of patient data listings that include, but are not limited to, tumor type, starting dose, tumor response at each visit, and best overall response. In addition, progression date, death date, date of first response and last tumor assessment date, and date of last contact will be listed.

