7. STATISTICAL METHODOLOGY AND STATISTICAL ANALYSES

7.1. Statistical Methods

The statistical summaries are non-inferential. The data are summarized by cohort defined by the initial dose of the study drug.

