7.1.3. Analyses for Binary endpoints

Binary data will be summarized using number of unique patient incidence, and confidence interval for binomial proportions may be presented

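### Table 7's 90% upper limit of 5.6% for 0/20 responders is too low (Jeffreys 9.0%, Wilson 11.9%, Clopper-Pearson 13.9%), and its footnote does not describe the calculation

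*Protocol*

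**What the plan says.** Protocol 9.3.1 disclaims a formal statistical basis for the Part A2 sample size. It then quotes power for 20 patients against a 2% response rate on current therapy, with true rates of 10% and 20%, and adds: "A table of 90% confidence intervals based on observed number of responders is provided below for reference". Table 7 follows, for N = 20:

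- 0 responders: 0 to 5.6%
- 1: 0 to 15.5%
- 2: 0 to 23.5%
- 4: 2.8 to 37.2%
- 6: 10.6 to 49.4%
- 8: 19.5 to 60.5%

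An asterisk on the zero row leads to the only remark on method: "with 0.005 continuity correction for confidence interval calculation". No interval method is named.

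Twenty is the planned arm size; Protocol 3.1.1.2 has dosing "given every 2 weeks up to 20 patients per arm". For reporting, Protocol 9.4 promises "Summary tables of response rates, median time to progression and corresponding confidence intervals will be provided". SAP 7.1.3 says only that a "confidence interval for binomial proportions may be presented", again without naming a method.

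**The concern.** An exact 90% upper limit for 0/20 leaves 5% in the upper tail: 1 − 0.05^(1/20) = 13.9%. The printed limit is well under half of that. A reader who takes it at face value would conclude that an arm with no responders has excluded every rate from 5.6% up, including the 10% rate for which the same paragraph quotes power. The footnote gives no way to see why the limit is so small, because applying 0.005 as a continuity correction does not reproduce the table.

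Low counts are plausible here. Protocol 3.1.1.2 reports one response among 10 patients at 0.1 mg/kg and one among 11 at 0.3 mg/kg. Table 7 is also the only worked response-rate interval in the two documents, so it is the natural template for the intervals promised in Protocol 9.4.

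**Working it through.** **Inputs.** n = 20 and the six printed rows (Protocol 9.3.1, Table 7); 90% taken as two-sided, z = 1.645; 0.005 from the footnote; 2% and 10% from the same section.

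**Reproducing the table.** The formula p ± [1.645·√(p(1−p)/20) + 1/40], truncated at 0, with p = 0.005 when there are no responders, gives:

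| Responders | p used | 1.645·√(p(1−p)/20) | Limits | Printed |
|---|---|---|---|---|
| 0 | 0.005 | 0.0259 | 0 to 5.59% | 0 to 5.6% |
| 1 | 0.05 | 0.0802 | 0 to 15.52% | 0 to 15.5% |
| 2 | 0.10 | 0.1103 | 0 to 23.53% | 0 to 23.5% |
| 4 | 0.20 | 0.1471 | 2.79 to 37.21% | 2.8 to 37.2% |
| 6 | 0.30 | 0.1685 | 10.65 to 49.35% | 10.6 to 49.4% |
| 8 | 0.40 | 0.1802 | 19.48 to 60.52% | 19.5 to 60.5% |

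All six rows match. Two alternatives do not:

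- Using 0.005 as the continuity correction matches no row: the upper limits are 0.5% (0/20), 13.5% (1/20), 21.5% (2/20) and 35.2% (4/20).
- Dropping the 1/40 term gives 3.1% (0/20, p = 0.005), 13.0%, 21.0% and 34.7%.

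The 0/20 limit depends on the substituted value. Putting 0.0025, 0.01 or 0.025 in place of 0.005 gives 4.6%, 7.2% or 10.7%.

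**Comparison with recognised 90% limits (%).**

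| Responders | Table 7 | Jeffreys | Wilson | Agresti-Coull | Clopper-Pearson |
|---|---|---|---|---|---|
| 0 | 0–5.6 | 0–9.0 | 0–11.9 | 0–14.1 | 0–13.9 |
| 1 | 0–15.5 | 0.9–18.0 | 1.1–19.6 | 0–20.9 | 0.3–21.6 |
| 2 | 0–23.5 | 2.9–25.0 | 3.4–26.2 | 2.5–27.0 | 1.8–28.3 |
| 4 | 2.8–37.2 | 8.7–37.3 | 9.3–37.8 | 8.9–38.2 | 7.1–40.1 |
| 6 (upper) | 49.4 | 48.2 | 48.4 | 48.5 | 50.8 |
| 8 (upper) | 60.5 | 58.2 | 58.1 | 58.2 | 60.6 |

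The likelihood-ratio limit at 0/20 is 1 − exp(−1.645²/40) = 6.5%, also above 5.6%. Before rounding, the 0/20 shortfall is 9.05 − 5.59 = 3.5 points against Jeffreys, 11.92 − 5.59 = 6.3 against Wilson and 13.91 − 5.59 = 8.3 against Clopper-Pearson.

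**Probability of 0/20.** At a true 5.6%: 0.944^20 = 0.316. At a true 10%: 0.9^20 = 0.122.

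**Coverage.** This is the sum of Binomial(20, p) probabilities over the counts whose interval contains p. For the Table 7 formula it is 68% just above 5.6%, 70% at 6%, 81% at 8% and 87% at 10%. On a 0.1% grid from 1% to 40%, mean (minimum):

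| Method | True rate 5.6–11% | Rest of 1–40% |
|---|---|---|
| Table 7 | 80.7% (68.0%) | 92.3% (83.4%) |
| Jeffreys | 90.6% (82.1%) | 90.1% (83.9%) |
| Wilson | 93.5% (88.1%) | 90.4% (80.2%) |

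In the 5.6–11% band Agresti-Coull has 94.9% (90.4%), Clopper-Pearson 97.1% (95.0%) and likelihood-ratio 82.3% (70.6%).

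**Lower side.** For 3/20, which is not printed, the formula gives 0 to 30.6% and so does not exclude 2%. The four tabulated methods do, with lower limits of 4.2% to 6.2%; P(3 or more of 20) at a true 2% is 0.7%.

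**The case against.** The strongest counter-argument is that nothing depends on the table. It is offered for reference, response is a secondary objective, SAP 7.1 states "The statistical summaries are non-inferential", and no Part A2 rule uses an interval. The Part B2 enrolment rule counts responders. This stands, and it keeps the point minor.

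Second, the 5.6–11% band starts exactly where the table's coverage drops. Over the whole 1–40% grid its mean coverage is 90.7%, close to Jeffreys (90.2%) and Wilson (90.9%). At a true 10% Jeffreys covers less (83.5% against 86.7%), and at 20% both Jeffreys (89.9%) and Wilson (84.4%) cover less than Table 7 (92.1%). This also stands. The defect lies in the upper limits at 0 to 2 responders, not in the whole table. From 2/20 upward the lower limits are below all four comparators, which is conservative for claiming activity.

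Third, recognised methods disagree on whether 0/20 excludes 10%: Jeffreys and likelihood-ratio exclude it, while Wilson, Agresti-Coull and Clopper-Pearson do not. That is true, but every one of them gives a limit above 5.6%.

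Fourth, the footnote does disclose the 0.005 and is attached only to the zero row. It is therefore mislabelled and incomplete rather than unrelated to the calculation, and 5.6% is not an arithmetic slip. That is fair. A reader still cannot rebuild the zero row or any other from what is printed.

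**Conclusion.** The concern holds, as a minor point. The 0/20 upper limit is low by 3.5 to 8.3 points against Jeffreys, Wilson and Clopper-Pearson, and by 1.0 point against even the likelihood-ratio limit. The 1/20 and 2/20 upper limits (15.5%, 23.5%) are also below the four tabulated methods (18.0–21.6% and 25.0–28.3%). The 6/20 and 8/20 upper limits are above Jeffreys, Wilson and Agresti-Coull and just below Clopper-Pearson. The footnote calls a substituted proportion a continuity correction, and neither the Wald method nor the 0.025 correction applied in every row is stated.

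The consequence is misread precision in an arm with few responders; no design decision changes. The conclusion assumes that the 90% intervals are two-sided and that the recipe inferred from the six matching rows is the one used.

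**What to change.** Replace the limits in Table 7 with Clopper-Pearson 90% limits:

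- 0/20: 0 to 13.9%
- 1/20: 0.3 to 21.6%
- 2/20: 1.8 to 28.3%
- 4/20: 7.1 to 40.1%
- 6/20: 14.0 to 50.8%
- 8/20: 21.7 to 60.6%

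Replace the footnote with the name of the method. Add one sentence stating that the same method, applied to the actual number of patients per arm, will be used for the response-rate intervals in Protocol 9.4. Naming it in SAP 7.1.3 as well is sensible, since the SAP takes precedence over the protocol's statistical text.

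Clopper-Pearson is proposed because it is the only one of the four tabulated methods with coverage of at least 90% at every true rate (minimum 90.05% over 0.1% to 99.9%). The price is conservatism: coverage of 97%, 98% and 96% at true rates of 6%, 8% and 10%. Sample size and conduct are unaffected.

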# 9.3.2. Part B Combination Therapy

The number of patients to be enrolled in the study will depend upon the observed safety profile, which will determine the number of patients at each dose combination level and the number of dose levels explored. The maximum sample size after which the Part B1 will be stopped and MTD declared is 55 patients. The total planned sample size for Part B2 expansion cohort is approximately 40 evaluable patients.

At least 9 patients each will be treated at the dose combination level(s) identified as MTD. If MTD was not reached by definition of safety criteria, this statement will apply for highest tested dose combination level

# 9.4. Efficacy Analysis

In this FIP study, anti-tumor clinical activity is a secondary objective.

Tumor response in terms of time to progression, tumor progression, duration of response, and best objective response by RECIST and irRECIST will be summarized. Summary tables of response rates, median time to progression and corresponding confidence intervals will be provided Summary tables and figures will be generated by dose levels and/or tumor types. Data will be presented in the form of patient data listings that include, but are not limited to, tumor type, starting dose, tumor response at each visit, and best overall response. In addition, progression date, death date, date of first response and last tumor assessment date, and date of last contact will be listed.

# 9.5. Analysis of Pharmacokinetics

# 9.5.1. PF-04518600 and Utomilumab PK Analysis

Serum pharmacokinetic parameters including the maximum concentration ( $C_{max}$ ), and area under the concentration versus time curve within a dose interval ( $AUC_{\tau}$ ) for PF-04518600 (Parts A and B) and utomilumab (Part B only) will be estimated using non-compartmental analysis. If data permit or if considered appropriate, minimum concentration ( $C_{min}$ ), average concentration ( $C_{av}$ ), AUC from time zero extrapolated to infinity ( $AUC_{inf}$ ), terminal elimination half-life ( $t_{1/2}$ ), clearance (CL), apparent volume of distribution ( $V_{ss}$ ), and accumulation ratio ( $R_{ac}$ ) will be also estimated. The PK parameters will be summarized descriptively by dose, and cycle.

The concentrations of PF-04518600 (Parts A and B) and utomilumab (Part B only) will be summarized descriptively by dose, cycle, and nominal time. Individual patient and median profiles of the concentration-time data will be plotted by dose and cycle using nominal times. Median profiles will be presented on both linear-linear and log-linear scales.

### 9.5.3. Immunogenicity

ADA samples will be analyzed for the presence or absence of anti- PF-04518600 and anti-utomilumab antibodies following a tiered approach using screening, confirmation and titer/quantitation using a validated assay. Samples tested positive for ADA will be further analyzed for NAb using a validated assay. Listings and summary tabulations of the time course data on immune response endpoints will be generated. Potential impact of immunogenicity on PK and clinical response including CCI safety/tolerability and efficacy of ADA will be explored, if data is warranted.

# 9.5.4. Statistical Analysis of Biomarker Endpoint

For biopsy samples, summary statistics (eg, the mean and standard deviation, median, and minimum/maximum levels of continuous, and frequencies and percentages of categorical biomarker measures) will be determined at baseline and post-treatment. For each pair of specimens, the percent change from baseline of these same parameters will also be calculated.

Data from biomarker assays may be analyzed using graphical methods and descriptive statistics such as linear regression, t-test, and analysis of variance (ANOVA). The statistical approach will examine correlations of biomarker results with pharmacokinetic parameters and measures of anti-tumor efficacy.

The percentage change from baseline for **CCl** over the period of the study will be tabulated by individual. The mean change from baseline values over time per cohort will also be tabulated. Data will be presented in tabular and/or graphical format and summarized descriptively.

# 9.6. Safety Analysis

Summaries and analyses of safety parameters will include all patients in the Safety Analysis Set.

### 9.6.1. Analysis of Primary Endpoint

Dose Limiting Toxicity (DLT) is the primary endpoint of the dose escalation component of the study. The occurrence of DLTs observed in the dosing cohorts is used to estimate the MTD as described in the Study Design Section 3. Adverse Events constituting DLTs will be listed per dose level.

# 9.6.2. Analysis of Secondary Endpoints

#### 9.6.2.1. Adverse Events

Adverse Events (AEs) will graded by the investigator according to the Common Terminology Criteria for Adverse Events (CTCAE) version 4.03 and coded using the Medical Dictionary for Regulatory Activities (MedDRA). The focus of AE summaries will be on Treatment Emergent Adverse Events, those with initial onset or increasing in severity after the first dose of study medication. The number and percentage of patients who experienced any AE, serious AE (SAE), treatment related AE, and treatment related SAE will be summarized according to worst toxicity grades. The summaries will present AEs both on the entire study period and by cycle (Cycle 1 and Cycles beyond 1).

# 9.6.2.2. Laboratory Tests Abnormalities

The number and percentage of patients who experienced laboratory test abnormalities will be summarized according to worst toxicity grade observed for each lab assay. The analyses will summarize laboratory tests both on the entire study period and by cycle (Cycle 1 and Cycles beyond 1). Shift tables will be provided to examine the distribution of laboratory toxicities.

For laboratory tests without CTC grade definitions, results will be categorized as normal, abnormal or not done.

#### 9.6.3. ECG

The analysis of ECG results will be based on patients in the safety analysis set with baseline and on-treatment ECG data. Baseline is defined as results collected at C1D1 prior to dosing. ECG measurements (an average of the triplicate measurements) will be used for the statistical analysis and all data presentations. Any data obtained from ECGs repeated for safety reasons after the nominal time-points will not be averaged along with the preceding triplicates. Interval measurements from repeated ECGs will be included in the outlier analysis (categorical analysis) as individual values obtained at unscheduled time points.

QT intervals will be corrected for heart rate (QTc) using standard correction factors [ie, Fridericia's (default correction), Bazett's, and possibly a study specific factor, as appropriate]. Data will be summarized and listed for QT, HR, response rate (RR), PR, QRS, QTcF (and other correction factors, eg, QTcB as appropriate), and by dose. Individual QT' (all evaluated corrections) intervals will be listed by time and dose. The most appropriate correction factor will be selected and used for the following analyses of central tendency and outliers and used for the study conclusions. Descriptive statistics (n, mean, median, standard deviation, minimum, and maximum) will be used to summarize the absolute corrected QT value and changes from baseline in corrected QT after treatment by dose and time point. For each patient and by treatment, the maximum change from baseline will be calculated as well as the maximum post-baseline value across time-points. Categorical analysis will be conducted for the maximum change from baseline in corrected QT and the maximum post-baseline QT value.

Shift tables will be provided for baseline vs worst on treatment corrected QT (one or more correction method will be used) using maximum CTC AE Grade. Shift tables will also be provided for ECG abnormality at baseline vs. on treatment (yes, no, not done: (n, %)). Patients experiencing clinically-relevant morphological ECG changes will be summarized (including frequency and percentage).

The effect of drug concentrations on corrected QT change from baseline will be explored graphically. Additional concentration-corrected QT analyses may be performed. Data may be pooled with other study results and/or explored further with PK/ pharmacodynamic models.

# 9.7. Analysis of Anti-drug Antibody (ADA) for PF-04518600 and Utomilumab

Summary of number of patients developed ADA for PF-04518600 and utomilumab will be tabulated by dose group. Subgroup analysis may be performed to assess the PK or pharmacodynamic response if data warrant.

# 9.9. Interim Analysis

There is no planned formal interim analysis.

#### 9.10. Data Safety Monitoring Committee

An external Data Safety Monitoring Committee will not be established for the study. For the purpose of this protocol, Pfizer procedures for periodic safety review will be applied by an internal safety review team with medical and statistical capabilities to review individual and summary data collected in the safety and clinical databases. Procedures include:

Surveillance for SAEs according to regulatory guidelines.

Discussions between the investigators and the sponsor of AEs and laboratory tests alterations seen at each dose level in an on-going manner at regular teleconferences and/or meetings to determine the safety profile and risk/benefit ratio and decide if further enrollment is appropriate.

# 10. QUALITY CONTROL AND QUALITY ASSURANCE

Pfizer or its agent will conduct periodic monitoring visits during study conduct to ensure that the protocol and Good Clinical Practices (GCPs) are being followed. The monitors may review source documents to confirm that the data recorded on CRFs are accurate. The investigator and institution will allow Pfizer monitors/auditors or its agents and appropriate regulatory authorities direct access to source documents to perform this verification. This verification may also occur after study completion.

During study conduct and/or after study completion, the study site may be subject to review by the institutional review board (IRB)/ethics committee (EC), and/or to quality assurance audits performed by Pfizer, or companies working with or on behalf of Pfizer, and/or to inspection by appropriate regulatory authorities.

The investigator(s) will notify Pfizer or its agents immediately of any regulatory inspection notification in relation to the study. Furthermore, the investigator will cooperate with Pfizer or its agents to prepare the study site for the inspection and will allow Pfizer or its agent, whenever feasible, to be present during the inspection. The study site and investigator will promptly resolve any discrepancies that are identified between the study data and the patient's medical records. The investigator will promptly provide copies of the inspection findings to Pfizer or its agent. Before response submission to the regulatory authorities, the investigator will provide Pfizer or its agents with an opportunity to review and comment on responses to any such findings.

It is important that the investigator(s) and their relevant personnel are available during the monitoring visits and possible audits or inspections and that sufficient time is devoted to the process.

